#### 1.0 PURPOSE

The purpose of the proposed study is to assess the safety and efficacy of the 17mm On-X Aortic Prosthetic Heart Valve when used to replace diseased aortic valves and the 23mm On-X Mitral Prosthetic Heart Valve when used to replace diseased mitral valves in human subjects.

The On-X 17mm aortic valve will be implanted in approximately 20 and at least 15 patients and will be followed for 1 year. Enrollment of On-X 23mm mitral valve patients has been discontinued due to low enrollment potential. Follow-up of enrolled patients will continue according to the protocol for 1 year.

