#### 2.0 PROTOCOL

This study is prospective. All centers will follow a common protocol in which eligible patients will be asked to participate in the 1-year follow-up of the On-X valve. The objective of the trial is to establish the clinical safety and effectiveness of the size 17mm aortic valve. It is expected that 20 centers from both within and outside the United States implanting between 1 to 2 valves will be involved. The number enrolled at a single center will depend entirely on the study as a whole reaching the required 15 patients. A copy of the investigator's agreement for the trial is contained in Appendix D.

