#### 2.1 STUDY DESIGN (SAMPLE SIZE)

Patients meeting all the appropriate criteria will be recruited for clinical trial participation. Enrollment is non-randomized, and continues until the sample size requirement is met, unless the sponsor terminates the clinical trial early for unforeseen reasons.

Submission for premarket approval in the U.S. will occur after international standards criterion of at least 15 patients will be followed for one year. This follow-up will include echocardiography, blood damage, NYHA status and any adverse events.

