At each center, patient recruitment will occur in the following manner. Determine whether or not the patient is eligible to receive the On-X valve by assessing if the patient meets the selection criteria. If the patient is eligible, discuss all aspects of the On-X clinical trial requirements and invite the patient or patient's legally authorized representative to participate. If the patient or representative agrees to participate, obtain informed consent and enroll the patient in the clinical trial. All patients who might receive a small valve should be consented even though a larger valve may be used based on findings during surgery. This may create some screen failures but will avoid losing potential patients in what is expected to be a small patient group overall.

Recruitment will continue until the overall study has reached its patient enrollment requirements.

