#### 2.4.3 Early Postoperative/Discharge Procedures

The investigator will record the date of the patient's discharge from the hospital and the date of the early follow-up examination on CRF4. The discharge follow-up exam records the patient's status at the time of discharge or at 30 days, whichever comes

first. The patient's NYHA and cardiac rhythm status and any complications will be noted along with the patient's antithromboembolic therapy. It is important to record the international normalized ratio (INR) at the time of the exam. Wherever possible this value should be within the therapeutic range described below **before** a patient is discharged from the hospital.

Mechanical heart valve recipients should be maintained continuously on anticoagulant therapy, except where contraindicated. Postoperatively, the continuous warfarin (tradename Coumadin®) therapy shall maintain the following therapeutic levels of INR: 2.0 to 3.0 for aortic valves. These procedures generally follow guidelines published by various medical societies.

Preoperative echocardiograms on the dysfunctional valve being replaced, predischarge, 3-6 month and one year postoperative Doppler echocardiograms on the study valve are required for each patient. At each postoperative assessment, the investigator will need to determine the patient's availability for future follow-up. If any patient needs to be seen at other than a regularly scheduled follow-up visit, the same follow-up information as required at regular times will be documented by the investigator on the follow-up form, and that follow-up will be indicated as an interim visit.

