#### 2. Exclusions

2.1 Poor echocardiographic window

#### 3. Recording studies

- 3.1 Unless impossible, every study will include the following standard imaging views: parasternal long-axis, parasternal short-axis, apical 4-chamber, apical 2-chamber, apical long-axis and subcostal. Off-axis views as appropriate will also be necessary particularly to look for paraprosthetic regurgitation.
- 3.2 Doppler recordings will be made with a stand-alone continuous wave probe from apical views and for valves in the aortic position from additional right intercostals or suprasternal views. Both orthograde waveforms and, if present, regurgitant jets will be recorded.
- 3.3 Subaortic pulsed recordings will be made in the apical 5-chamber view with the sample placed just below the level at which significant flow acceleration occurs.
- 3.4 Recordings should be made with the scale set to maximize signal size and with the maximum available sweep speed.
- 3.5 All images and waveforms used for calculating information will be recorded on electronic media.

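### Does the plan leave open which patients count toward the required 15?

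*Combined protocol and SAP*

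**What the plan says.** Four places mention the target for the 17mm aortic valve.

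- Section 1.0: "The On-X 17mm aortic valve will be implanted in approximately 20 and at least 15 patients and will be followed for 1 year".
- Section 2.0: "The number enrolled at a single center will depend entirely on the study as a whole reaching the required 15 patients".
- Section 2.1: "Enrollment is non-randomized, and continues until the sample size requirement is met". The U.S. submission "will occur after international standards criterion of at least 15 patients will be followed for one year", and the content of the follow-up is then listed: "This follow-up will include echocardiography, blood damage, NYHA status and any adverse events".
- Section 2.2, recruitment paragraph: "Recruitment will continue until the overall study has reached its patient enrollment requirements".

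Two sections on procedures bear on what one year of follow-up means. Section 2.4.3 requires, for each patient, preoperative and predischarge echoes and "3-6 month and one year postoperative Doppler echocardiograms on the study valve". Section 2.4.4 places the one-year visit between 11 and 14 months, requires it to be in person and rules out telephone contact. It also makes CRF 4 due at every scheduled time, even when no visit took place.

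Two places do not sit well with these. Appendix A, under Exclusions, has the single entry "2.1 Poor echocardiographic window", which is not among the 14 exclusion criteria in section 2.2. CRF 4 in Appendix B offers Telephone as a type of examination.

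**The concern.** The units are not interchangeable. Section 2.2 has patients consented before the valve size is known, so some enrolled patients will not receive a 17mm valve. An implanted patient may die, be explanted (section 2.2 then treats a survivor as withdrawn) or miss the one-year visit. A target of 15 enrolled, 15 implanted and 15 followed for a year could be met at three different times.

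The echo entry and the Telephone box seem to widen the gap. If a poor window excludes only the exam, a patient could be implanted and followed for a year without usable hemodynamics. If a telephone contact could pass as the one-year visit, there would be neither echo nor blood sample. The submission could then claim 15 patients followed while holding fewer than 15 one-year echo and blood sets. Section 4.0 names hemodynamic and blood damage data as what is lacking for U.S. availability, so these are the data that matter most.

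**Working it through.** **1. Is there a governing rule?**

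| Place | Wording of the target | What it adds |
|---|---|---|
| 1.0 | about 20 and at least 15 implanted, followed for 1 year | planned number and minimum |
| 2.0 | required 15 | refers to a requirement set elsewhere |
| 2.1 (Sample Size) | at least 15 followed for one year | echo, blood, NYHA, adverse events |
| 2.2 | enrollment requirements | refers to a requirement set elsewhere |
| 2.4.3 | each patient | one-year echo |
| 2.4.4 | late follow-up | in person, 11 to 14 months, blood sample |

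Only section 2.1 describes what must be achieved, and it does so under the sample size heading. Section 1.0 also couples its number with a year of follow-up. Sections 2.0 and 2.2 define nothing that competes. Read together, a patient counts after an in-person visit at 11 to 14 months with the four listed components. A patient withdrawn after an early explant has not been followed for one year and does not count.

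**2. Is the margin reasonable?** The 15 comes from an international standard and has no power calculation to reproduce. The allowance implied by 20 implants is 1 − 15/20 = 25%, or 5 patients. The documents give no loss rate, so the rates below are assumed. With total loss d, the chance of at least 15 countable patients among 20 is P(X ≥ 15), X ~ Binomial(20, 1 − d):

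| d | 5% | 10% | 15% | 20% | 25% |
|---|---|---|---|---|---|
| P | 0.9997 | 0.989 | 0.933 | 0.804 | 0.617 |

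Combining attrition with incomplete data among attenders, countable share = (1 − attrition) × (1 − incomplete):

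- 10% and 5%: 0.90 × 0.95 = 0.855, P = 0.94.
- 10% and 10%: 0.90 × 0.90 = 0.81, P = 0.84.
- 15% and 10%: 0.85 × 0.90 = 0.765, P = 0.68.

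Stopping at exactly 15 implants would leave no room: 0.95^15 = 0.463 and 0.90^15 = 0.206. Section 2.1 does not plan that, since enrollment goes on until the requirement is met.

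**3. What would miscounting cost?** Suppose 15 were claimed but 1, 2 or 3 lacked an echo. The 95% CI half-width of a mean, in SD units, is t(0.975, n − 1)/√n: 0.554 at n = 15, then 0.577, 0.604 and 0.635 at n = 14, 13 and 12. The intervals are 4, 9 and 15% wider. The reported n would show this.

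**4. The two mismatches.** CRF 4 serves the discharge, 3-6 month, 1-year and off-schedule visits, has a lost-to-follow-up entry and an echo completion date, and is due even without a visit. A Telephone box lets a site record a contact that does not meet section 2.4.4, and labels it as such. The Appendix A entry stands between observer variability and recording instructions, where excluding an exam is at least as natural as excluding a patient. Nearby text handles unobtainable measurements the same way, by leaving them blank or not making them.

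**The case for a change.** The best case for acting is that the rule has to be assembled from three sections. No sentence says whether a patient with an unusable one-year echo, a missing blood panel or a visit outside the window counts. Nothing states what the Telephone box is for, or whether a poor window excludes the patient or the exam. Section 1.0, read alone, permits 15 implants, which meet section 2.1 only with no loss at all. A few words would settle all this at almost no cost.

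The two mismatches are real, and a line of explanation at each would be good housekeeping. The text does not spell out the handling of incomplete patients. The step to harm does not stand: it needs the sponsor to count patients without echo or blood data although section 2.1 lists both as part of the follow-up. Monitoring under section 2.4.9 gives particular attention to echocardiography and blood studies and checks that missed visits are documented. A stricter rule demanding complete data for every counted patient might also require a few more implants. The documents do not show that the standard behind the 15 asks for it.

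**Conclusion.** The concern does not call for a change. Section 2.1, with sections 2.4.3 and 2.4.4, gives a workable rule, and an analyst following it would count the right patients. The looser wording in sections 1.0, 2.0 and 2.2 does not contradict it, and the Appendix A entry and the CRF 4 box are clerical matters that can be tidied when those pages are next revised.

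No stated figure is wrong. The 20 or so planned implants keep the chance of 15 countable patients at 0.90 or more up to about 16.6% total loss. That is a fair margin, given entry criteria that select patients likely to survive a year and willing to return. If losses were heavier, enrollment would continue and submission would come later; no estimate would be biased by that. These probabilities rest on assumed loss rates and independent losses. The conclusion itself rests on reading the sample size requirement as section 2.1 states it.

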#### 2.0 PROTOCOL

This study is prospective. All centers will follow a common protocol in which eligible patients will be asked to participate in the 1-year follow-up of the On-X valve. The objective of the trial is to establish the clinical safety and effectiveness of the size 17mm aortic valve. It is expected that 20 centers from both within and outside the United States implanting between 1 to 2 valves will be involved. The number enrolled at a single center will depend entirely on the study as a whole reaching the required 15 patients. A copy of the investigator's agreement for the trial is contained in Appendix D.

#### Valve safety:

- Although sample size will limit the value of event rate calculations, early (30-day) and late time-related incidence and associated rate of all deaths and each valve related cardiovascular complication will be determined. Adverse events are those defined by the STS/AATS definitions, as well as all other cardiovascular complications. Rates of valve thrombosis, thromboembolism, hemorrhage (both all and major), endocarditis, hemolysis, hemolytic anemia, mortality, reoperation, valve explantation and prosthetic valve dysfunction (structural, non-structural and paravalvular leak (both all and major)) are primary safety endpoints to be evaluated using both linearized and actuarial statistical methods.
- Hemolytic potential of the valve will be measured using a CBC, reticulocyte count, serum haptoglobin, serum lactate dehydrogenase and plasma free hemoglobin.

#### Valve effectiveness:

• Functional status changes will be assessed using classification nomenclature developed by the New York Heart Association (NYHA). The assessment

shall include proportions within class and cross tabulation of changes over time.

• Hemodynamic performance of the valve will be determined by echocardiography. The following specific parameters will be evaluated using standard descriptive statistics: peak and mean pressure gradients, effective orifice area (EOA), cardiac output (CO), valvular regurgitation and indices of EOA and CO to body surface area (BSA), and performance index of EOA to geometric orifice area (GOA).

Valve safety and effectiveness will be compared by valve position to corresponding historical controls contained in the clinical results presented in the original PMA for other size On-X valves (P000037 and P000037/S001). The trial is designed specifically to meet the criteria established by ISO and recognized by FDA for clinical trials of a single size of a prosthetic heart valve. The data will be used to obtain and maintain appropriate regulatory approvals where needed.

#### 2.1 STUDY DESIGN (SAMPLE SIZE)

Patients meeting all the appropriate criteria will be recruited for clinical trial participation. Enrollment is non-randomized, and continues until the sample size requirement is met, unless the sponsor terminates the clinical trial early for unforeseen reasons.

Submission for premarket approval in the U.S. will occur after international standards criterion of at least 15 patients will be followed for one year. This follow-up will include echocardiography, blood damage, NYHA status and any adverse events.

#### 2.2 PATIENT POPULATION AND SELECTION CRITERIA

The indications for replacement of a patient's natural or prosthetic valve will be those which the principal investigator follows in his routine practice of cardiovascular surgery.

The following are criteria for inclusion of patients in this study:

- 1. Patients of any age; unless waived by local IRB assent of the patient and in all cases consent of parent or legally authorized representative is required if a patient is under the age of majority and not legally emancipated.
- 2. Patients who are sufficiently ill to warrant replacement of their diseased natural or prosthetic valve, based on standard cardiovascular diagnostic workups.
- 3. Patients who are in sufficient satisfactory condition, based on the physical exam and investigator's experience, to be an average or better operative risk, (i.e., likely to survive one year postoperatively).
- 4. Patients who require an isolated aortic valve replacement size 17 mm.
- 5. Patients who are geographically stable and willing to return to the implanting center for follow-up visits.

- 6. Patients or legally authorized representatives who are adequately informed of their participation in the clinical study and what will be required of them in order to comply with the protocol.
- 7. Patients requiring concomitant cardiovascular surgery, such as coronary bypass may be included in the study.

#### The following are criteria for exclusion of patients from this study:

- 1. Patients who are pregnant, planning to become pregnant or are lactating.
- 2. Patients who have a noncardiac progressive disease, which in the investigator's experience produces an unacceptable increased risk to the patient.
- 3. Patients who have a documented history of substance (drug or alcohol) abuser or are prison inmates.
- 4. Patients with a previous prosthetic valve, where it is not being replaced by a study valve, or patients requiring multiple valve replacement.
- 5. Patients with active endocarditis or active myocarditis.
- 6. Patients who require mitral, tricuspid or pulmonic valve replacement.
- 7. Patients who have not agreed to return for the required number of follow-up visits or who are geographically unavailable for follow-up.
- 8. Patients who cannot be maintained on long-term anticoagulant therapy.
- 9. Patients with non-cardiac illness resulting in a life expectancy of less than 1-year.
- 10. Patients previously enrolled and implanted in this trial may not re-enter after withdrawal.
- 11. Patients already enrolled in another investigational device or drug study (nor can enrolled patients be enrolled in other studies).
- 12. Patients with acute preoperative neurological deficit, myocardial infarction, or cardiac event who have not returned to baseline for at least 30-days prior to enrollment.
- 13. Patients with aortic aneurysm or other medical condition that creates a higher than usual risk of surgical complication.
- 14. Patients who are prisoners or mentally ill, and pediatric patients of assent age who are incapable of understanding their assent as judged by the principal investigator.

Patients are free to withdraw from the study at any time for any reason without prejudicing their medical care. Surviving patients who have their valve explanted for any reason will also be considered withdrawn. There are no other anticipated reasons for withdrawal from the study.

At each center, patient recruitment will occur in the following manner. Determine whether or not the patient is eligible to receive the On-X valve by assessing if the patient meets the selection criteria. If the patient is eligible, discuss all aspects of the On-X clinical trial requirements and invite the patient or patient's legally authorized representative to participate. If the patient or representative agrees to participate, obtain informed consent and enroll the patient in the clinical trial. All patients who might receive a small valve should be consented even though a larger valve may be used based on findings during surgery. This may create some screen failures but will avoid losing potential patients in what is expected to be a small patient group overall.

Recruitment will continue until the overall study has reached its patient enrollment requirements.

#### 2.2.1. Screen Failures

The principal investigator will select patients to approach for enrollment based on his professional judgment using all available preoperative data. It is not expected that large patients (body surface area (BSA)>1.8M²) or patients with echo finding of native valve diameters greater than 19mm aortic will be screened as candidates, but those with small body size <1.5M² or smaller than the above valve diameters by echo will be screened. All patients approached or evaluated for enrollment will be entered on the screening log contained in the case report forms in Appendix B. If prior to surgery the patient is dropped from consideration or during surgery a different valve is implanted, then the screen failure will be noted in the log with sufficient explanation to allow assessment of the cause of the screen failure and determination of affect on the study.

#### 2.3 INSTITUTIONAL REVIEW AND INFORMED CONSENT

Institutional review through the appropriate standing committee of the clinical center (either Ethics Committee or Institutional Review Board) must be obtained as required by local rules, and a copy of the approval document must be supplied to the sponsor. A list is contained in Appendix F.

Informed consent must be obtained for each patient prior to participation in the clinical trial in accordance with local rules. As this study includes some pediatric patients, consent shall include assent of the patient as well as consent of his/her parent or legally authorized representative whenever such patient is recruited. Assent may be waived by the local IRB if the patient is incapable due to age, maturity or psychological state. Local IRB rules or individual case review can be used to determine if waiver is appropriate, which if not addressed in the IRB approval document must be obtained case-by-case. It is the responsibility of the principal investigator to obtain such waiver prospectively as needed. A copy of the informed consent should be provided to the patient or representative and they should be encouraged to review it. It is recommended that the informed consent be reviewed as part of the preoperative procedures with prospective enrollment. An example informed consent document is in Appendix C.

Each clinical center must have a staff echocardiologist responsible for conduction of the echocardiographic portions of this study. Additionally, coagulation profiles are to be reported as the international normalized ratio (INR), and hemolysis study blood samples must be sent to a local laboratory and the laboratory normal ranges must be supplied to the sponsor.

This study also requires that copies of all echocardiography electronic recordings be sent to the sponsor for review.

#### 2.4 INVESTIGATIONAL PROCEDURES

The sponsor will provide case report forms (CRFs) to each principal investigator for the purpose of recording patient data. Assessments will be obtained for the preoperative, operative/discharge period and postoperatively at three to six months and one year from the date of implant (Table 2.4.1 summarizes the required information at each visit).

Table 2.4.1 - Patient Progress and Data Record

Interval of Follow-up
Preoperation Operation Early/discharge 3-6 1 Year
Month

#### Form/Data

Preoperative Form CRF 1
Echocardiography CRF 2
Echo Recordings
Blood Sample to Lab
Implantation Data Card
Operative Form CRF 3
Early Follow-up CRF 4
Late Follow-up CRF 4
Complication CRF 5
Reoperative CRF 6
Death Summary/ Autopsy
Explant Summary

Х				
Х		Х	Х	Х
X		Х	Х	Х
0			Х	Х
	Χ			
	Χ			
		Х		
			Х	Х
	0	0	0	0
	0	0	0	0
	0	0	0	0
	0	0	0	0

Χ	Required	Data
0	Required	only if needed
	Not	applicable

All appropriate sections of the CRFs must be filled out accurately and completely. Echocardiography recordings are to be forwarded to the sponsor for eventual assessment by a core cardiologist. All case report forms must be reviewed, signed and dated by the investigator(s). The CRFs should be sent expeditiously to the sponsor, when completed, and be kept in the patient record notebooks. Blood samples for hemolysis assessment are to be properly forwarded to the laboratory, per its protocol.

To protect patient confidentiality, the sponsor will use the information from the CRF's for statistical and device tracking purposes only and will treat medical records as confidential. For this reason, the sponsor is not routinely collecting patient names, but using patient initials for patient identification; thus better protecting patient confidentiality. A representative of the U.S. Food & Drug Administration or other appropriate regulatory authority may look at, and perhaps copy, some of the medical records; these organizations also have rules for protection of patient privacy that they must follow.

